7.8.2 Laboratory data

The analyses of laboratory data will be descriptive in nature and will be based on BI standards (8). Note that data from the central Laboratory will be used for all displays described below, unless otherwise specified.

For continuous safety laboratory parameters, normalized values will be derived. Normalisation means transformation to a standard unit and to a standard reference range. The process of normalisation, handling of repeat values at the same visit for by-visit displays, as well as standard analyses for safety laboratory data are described in the BI guidance for the Display and Analysis of Laboratory Data (8). All analyses considering multiple times of the ULN (as described below) will be based on standardized and not normalized values. For continuous safety laboratory parameters, differences to baseline will be calculated. For all outputs, the last assessment before the first randomized treatment at Day 1 is chosen as the baseline value.

Only patients with at least one available post-baseline value will be included in the analysis of an individual laboratory parameter. All individual laboratory data will be listed. Values outside the reference range will be flagged.

Descriptive statistics of laboratory values and for the difference from baseline on-treatment (see Section 6.7) will be based upon standardized values and provided by visit. In primary analysis, all visits up to week 16 will be reported including summaries of the last value, the minimum value and the maximum value up to week 16 based on SAF. In final analysis, all visits will be reported including summaries of the last value, the minimum value and the maximum value on treatment period for Arm 1-4 and, up to and post the first treatment at or after week 16 respectively for Arm 5 based on SAF.

Laboratory values will be compared to their reference ranges; shift tables will be provided for the number of patients with a specific RCTC grade at baseline versus the grade at the last measurement, as well as the worst grade. In particular, for shift tables in final analysis, the last measurement and the worst graded will be counted by the period up to and post the first treatment at or after week 16 respectively for Arm 5.

Potentially clinically significant abnormalities will be identified based on BI standard rules which are based on normalized converted lab values, i.e. using SI units. These rules will be listed in the SDL appendix of the CTR. Frequency tables will summarize the number of patients with potentially clinically significant abnormalities. Patients having an abnormal lab value at baseline will be presented separately. A separate listing will present potentially clinically significant abnormal lab values; for each functional lab group all patient's lab values will be listed, if there exists at least one lab value with clinically significant abnormality within the group.

The frequency of patients with AST or ALT elevations $\geq 3xULN$, $\geq 5xULN$, $\geq 10xULN$, and $\geq 20xULN$ will be displayed based on standardized laboratory values. To support analyses of

liver related adverse drug effects, the frequency of patients with AST and/or ALT $\geq 3xULN$ combined with a total bilirubin $\geq 2xULN$ in a 30 day period after AST/ALT elevation will be displayed, stratified by alkaline phosphatase $< 2xULN$ and $\geq 2xULN$ (a patient can potentially be in both alkaline phosphatase strata in case of multiple AST/ALT and bilirubin elevations). The start of the 30 day time span is triggered by each liver enzyme elevation above the defined thresholds. This analysis will be based on standardized laboratory values. A graphical analysis of the ALT and total bilirubin during the on-treatment period will also be performed; the so called eDISH plot. In the graph, for each subject, the peak total bilirubin is presented as a fold increase over the ULN against the peak ALT as a fold increase over the ULN, on a log10 scale. The measurements displayed of total bilirubin and ALT may, or may not, occur on the same date. Two reference lines, $2xULN$ for total bilirubin and $3xULN$ for ALT, are drawn onto the graph in order to divide the plane into four quadrants. Normal cases are in the lower left quadrant, potential DILI cases are in the upper right quadrant (Hy's Law quadrant), while the lower right quadrant is known as the Temple's corollary range (ALT $\geq 3xULN$ and total bilirubin $< 2xULN$).

Clinically relevant findings in laboratory data will be reported as baseline conditions (at screening) or as AEs (during the trial) if judged clinically relevant by the investigator, and will be analyzed as such.

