The primary analysis is planned to be performed once all patients have completed through the planned first 16 weeks of trial or early discontinued. The primary analysis will focus on individual patient's data up to treatment at week 16. If a patient early discontinued from treatment before week 16 or missed visit at week 16 but was still ongoing beyond week 16, all on-treatment data up to Day 127 which is the right limit of the week 16 extended time window (see [Table 6.7: 1](#)) will be included. In addition, for patients who missed visit at week

16 but was still ongoing beyond week 16, PPP Pain VAS, PPP ASI and PPP PGA assessments up to the first maintenance treatment after Week 16 (if available at time of primary analysis) will be included. They will not be reported in any outputs for primary analysis but might be used for imputation of endpoints related to PPP Pain VAS, PPP ASI and PPP PGA. See [Section 6.6.2](#) for the details of imputation methods.

The final trial analysis is planned to be performed at the end of the study once all randomized patients have completed the study (including any applicable follow-up period). The final trial analysis will include all trial data.

Treatment groups for the analysis of Arm 1-4 will be labelled and sorted as follows:

- **"Speso Low"**: (i.e., Arm 4)
- **"Speso Medium-low"**: (i.e., Arm 3)
- **"Speso Medium-high"**: (i.e., Arm 2)
- **"Speso High"**: (i.e., Arm 1)
- **"Speso Total"** (i.e., Arm 1, 2, 3 and 4), where appropriate for analysis up to Week 16

Treatment groups for Arm 5 will be labelled differently based on the data included in the analysis:

- **"Placebo & Speso"**: (i.e., Arm 5 if all trial data reported)
- **"Placebo"**: (i.e., Arm 5 if only data prior to the first Spesolimab treatment reported)
- **"Speso post placebo"**: (i.e., Arm 5 if only data post the first Spesolimab treatment reported)

If needed, Arm 1-5 could be pooled using the following label:

- **"Overall Total"**: (i.e., Arm 1, 2, 3, 4 and 5), where appropriate

For the analysis on safety data post Week 16, the following treatments will be added in addition to original treatments as follows (see [Section 7.8](#)):

- **"Speso [REDACTED]"** (i.e., Arm 1 + Arm 3 + Arm 5)

For the additional analysis on efficacy and safety data within loading stage, treatments will be re-grouped as follows (see [Section 7.6.4](#) and [Section 7.8](#)):

- **"Placebo"**: (i.e., Arm 5)
- **"Speso [REDACTED]"** (i.e., Arm 3 + Arm 4)

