If a patient is randomized but not treated, they will not be included into efficacy or safety analysis according to FAS (including FAS-post 16), m-FAS, PPS and SAF (including SAF-post 16).

If a patient is treated but not randomized, they will be excluded from both efficacy analysis and safety analysis by definition. However, patients under such circumstances will be described separately in the final clinical trial report.

If a patient is randomized but took incorrect treatment during the study, then:

- For efficacy analyses according to FAS (including FAS-post 16), m-FAS and PPS, they will be reported under their randomized treatment groups.
- For safety analyses using the SAF,
 - For Arm1-4: If a patient is planned to receive multiple dose administrations of Spesolimab, then patients will be reported under their randomized treatment group for safety analysis because the overall safety profile is expected to be driven by the amount of Spesolimab received in totality over the entire treatment duration. It is not expected that the safety profile will deviate from the planned treatment regimen if the subject receives only a few vials of the incorrect medication at only some dosing occasions.
 - For Arm 5: If a patient is planned to receive multiple dose administrations of placebo (prior to Week 16 only), then patients will be reported under their randomized treatment group for safety analysis if the patient receives no dose of randomized Spesolimab during this treatment period (i.e., prior to Week 16). If the patient receives ≥ 1 syringe of randomized Spesolimab during this treatment period, then the patient will be assigned to Arm 4 (lowest dose of Spesolimab planned in the trial before week 16).
- For safety analyses using the SAF-post 16,
 - For Arm1-5: If a patient is planned to receive multiple dose administrations of Spesolimab, then patients will be reported under their randomized treatment group for safety analysis because the overall safety profile is expected to be driven by the amount of Spesolimab received in totality over the entire treatment duration. It is not expected that the safety profile will deviate from the planned treatment regimen if the subject receives only a few vials of the incorrect medication at only some dosing occasions.

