6.7 BASELINE, TIME WINDOWS AND CALCULATED VISITS

Measurements reported with date and time and taken prior to start of administration of trial treatment will be considered pre-treatment values. Measurements reported with a date only (and no time) and taken on the day of first administration of trial treatment will also be considered pre-treatment values. These pre-treatment values will be assigned to visits according to the nominal visit number as recorded on the eCRF or as provided by the laboratory.

Baseline, unless otherwise specified, is defined as the last measurement collected prior to the start of administration of the trial treatment.

Measurements taken after start of administration of trial treatment will be considered either on- or off-treatment values based on the definition in [Section 6.1](#), and will be assigned to visits for statistical analysis, if applicable, as defined below.

Analysis of AE data, potentially clinically significant abnormal laboratory values, concomitant medication or non-drug therapies, as well as use of rescue therapy will not be based on visits. Frequency tables for these data will be using on-treatment data and categorized based on their occurring/starting dates. Therefore, no assignment to time windows will be necessary for such data.

The derivation of the last value, minimum value and maximum value of laboratory and vital signs data will consider all on-treatment values (whether or not selected in any time window; see [Table 6.1: 1](#) for definition of the on-treatment period) within the period of interest; these will be derived for analysis of laboratory and vital signs data.

All other safety, efficacy XXXXXXXXXX measurements will be assigned to visits based on extended time windows around the planned visit dates, defined relative to the day of first trial

treatment (which is scheduled for Visit V2). These extended time windows are defined in [Table 6.7: 1](#).

Table 6.7: 1 Time windows for assignment of efficacy, safety lab, vital XXXXXXXXXX measurements to visits for statistical analysis

Visit number / name	Visit label	Planned day	Time window (Days)				
			Window (per CTP)	Start (per CTP)	End (per CTP)	Start (extended)	End (extended)
V1	Screening	- 28 to - 14					
V2	Day 1	Day 1		1 ^A	1	1 ^A	1
V3	Week 1	Day 8	+/- 2	6	10	2	11
V4	Week 2	Day 15	+/- 2	13	17	12	18
V5	Week 3	Day 22	+/- 2	20	24	19	25
V6	Week 4	Day 29	+/- 2	27	31	26	43
V7	Week 8	Day 57	+/- 7	50	64	44	71
V8 ^C	Week 12	Day 85	+/- 7	78	92	72	99

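### Arm 5 laboratory and vital-sign differences after the switch to spesolimab are taken from the Day 1 pre-placebo value, so they mix change on placebo with change on drug

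*SAP*

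**What the plan says.** SAP 7.8.2 (Laboratory data) states the baseline rule without exception: "For all outputs, the last assessment before the first randomized treatment at Day 1 is chosen as the baseline value". For vital signs, SAP 7.8.3 refers to SAP 6.7, where the default reads: "Baseline, unless otherwise specified, is defined as the last measurement collected prior to the start of administration of the trial treatment". For Arm 5 both rules point to the value before the first placebo dose.

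The SAP elsewhere treats Arm 5 as two treatments in sequence. SAP 6.3 describes its placebo dosing as running only before Week 16. SAP 6.1 gives it a separate label for the later data ("i.e., Arm 5 if only data post the first Spesolimab treatment reported"). In the final analysis, Arm 5 last, minimum and maximum values are reported separately before and after the switch, for laboratory data (7.8.2) and vital signs (7.8.3). For the laboratory shift tables, the last and worst toxicity grades "will be counted by the period up to and post the first treatment at or after week 16 respectively for Arm 5". Only the post-baseline side is split; the baseline grade is not.

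For potentially clinically significant laboratory abnormalities, SAP 7.8.2 adds: "Patients having an abnormal lab value at baseline will be presented separately". SAP 7.8 reports these abnormalities after the switch by arm and for Arms 1, 3 and 5 pooled.

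**The concern.** Splitting Arm 5 at its first spesolimab dose is useful because it separates placebo data from active-drug data. A Day 1 reference partly undoes that. For Arms 1-4, Day 1 is the last value before spesolimab; for Arm 5 it lies about 16 weeks and several placebo doses earlier. The same column heading, difference from baseline, then means different things in different arms.

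Arm 5 is planned at 40 of 140 patients. It is the only arm in which a patient's values off drug can be set against the same patient's values on drug, and it feeds the pooled Arm 1+3+5 abnormality column. At stake is how a descriptive safety table is read: placebo-period change can be taken for a drug change, or can cancel one.

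**Working it through.** The plan states no figure on this point, so there is none to reproduce. The check has three parts.

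**1. Differences from baseline.** For any Arm 5 value at time t after the switch:

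(value at t − Day 1) = (value at t − Week 16 pre-dose) + (Week 16 pre-dose − Day 1)

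The last term is change on placebo. It enters every post-switch difference in full and can have either sign. With assumed values of 20 on Day 1, 30 at Week 16 pre-dose and 32 later:

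- As planned: 32 − 20 = +12 in the post-switch period.
- From the pre-switch value: 32 − 30 = +2.
- The remaining 30 − 20 = +10 arose on placebo.

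**2. Shifts and baseline status (laboratory only).** Take a patient with grade 0 on Day 1 who reaches grade 1 on placebo and stays there. The planned post-switch table shows a 0-to-1 shift; from the pre-switch value it is 1-to-1, no shift. Likewise, a potentially significant abnormality that began on placebo and persists is not classed as abnormal at baseline. An abnormality that has resolved by the later measurement is not carried over.

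**3. Size, by simulation.** The documents give no distribution for any laboratory parameter, so every input is an assumption:

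- 14 four-weekly values per patient (Day 1 to Week 52), 200,000 patients per setting, no drug effect;
- 10% of values abnormal at the start;
- underlying four-week correlation 0.90 to 0.95, with 10-20% of the variance as visit noise;
- drift over the placebo weeks of 0, +0.3 or −0.3 SD (positive is toward abnormal), then flat.

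Normal-to-abnormal shifts at Week 52, per 40 patients:

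| Placebo drift | Day 1 baseline | Week 16 baseline |
|---|---|---|
| none | 2.8-3.3 | 2.5-3.1 |
| +0.3 SD | 4.8-5.5 | 3.6-4.6 |
| −0.3 SD | 1.5-1.9 | 1.6-1.9 |

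Ranges run over the correlation and noise settings. The share of Day 1-based shifts already abnormal at Week 16 is about 16-23% without drift and about 24-32% with +0.3 SD. That share is gross. Rebasing also adds patients who were abnormal on Day 1, normal at Week 16 and abnormal later, so without drift the net fall is only about 0.2-0.3 patients of 40. With +0.3 SD drift, the mean difference in the active period is about 0.30 SD although the simulated drug effect is 0.

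**Feasibility and the SAP's own practice.** The protocol Flow Chart schedules safety laboratory and vital signs at Visit 9 (Week 16). Protocol 6.2.2 places blood draws before dosing, and Flow Chart note 7 requires pre-dose vital signs. SAP 7.5.3 already uses Week 16 as baseline for the later PPP ASI analysis.

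**The case against.** Four objections carry weight.

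- **Nothing is concealed.** Laboratory values and differences are tabulated by visit, including Week 16; the placebo period is summarised separately; all individual laboratory data are listed. This stands for group-level drift. It does not let a reader remove the placebo part from the post-switch last, minimum and maximum differences or from the shift tables without returning to patient listings.
- **The stakes are limited.** Safety analysis is descriptive with no hypothesis tests, and the SAP does not itself call these differences drug effects. Outputs based on multiples of the upper limit of normal and the eDISH plot use no baseline. Findings judged clinically relevant become adverse events, which are assigned to periods by start date. All of this stands. Vital signs have no planned shift table or abnormality split, so for them only the differences are affected.
- **One rule for all arms is simpler.** Giving Arm 5 a second baseline puts two calendar time points into the pooled Arm 1+3+5 column. That is true, but defined as the last value before first spesolimab, the baseline has the same meaning in every arm of that column. Under the current rule it does not.
- **The bias need not run against the drug.** A reader might infer that Day 1 always inflates apparent harm. The documents do not support that: the placebo term has no fixed sign, and under improvement on placebo the Day 1 baseline gives slightly fewer shifts.

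**Conclusion.** The point holds for Arm 5 outputs after the first spesolimab dose: laboratory differences, laboratory shift tables, abnormal-at-baseline status, and vital-sign differences. That each difference contains the full net placebo-period change follows from the definitions and needs no assumption.

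The numerical effect does rest on assumptions. Without drift it is largely a reclassification of individual patients with little net change in counts. A fall of roughly one shift in 40 patients arises only under the assumed +0.3 SD drift, for which the documents give no basis. It would be wrong to conclude that the safety tables are invalid, that drift is hidden, or that the Week 16 primary analysis is touched. The change should be made because the present rule blurs the split that the SAP makes and the remedy is cheap.

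**What to change.** In SAP 7.8.2 and 7.8.3, state that for Arm 5 outputs after the first spesolimab dose, baseline is the last value before that dose (Week 16 pre-dose where available, otherwise the last earlier value). Apply it to differences from baseline, laboratory shift tables and abnormal-at-baseline status. Keep Day 1 for the Arm 5 placebo period and for Arms 1-4. The default in SAP 6.7 already allows exceptions, so a cross-reference there is enough.

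Footnote the pooled Arm 1+3+5 abnormality column: baseline is the last value before first spesolimab in every arm, which is Day 1 for Arms 1 and 3 and Week 16 pre-dose for Arm 5.

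The cost is SAP wording, one derived baseline variable and the footnote. No new data are needed, and SAP 7.9 already foresees a revision before the final analysis. The downside is that Arm 5 carries two baselines, which table titles must make clear.

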3. DESCRIPTION OF DESIGN AND TRIAL POPULATION

3.1 OVERALL TRIAL DESIGN AND PLAN

This is a randomised, double-blind, placebo-controlled, parallel-design dose-finding trial comprising of 4 active doses compared to placebo. Active treatment arms consist of active loading dose and active maintenance treatment. Two different loading doses and two different maintenance treatment doses are to be tested up to Week 16 (to give four different BI 655130 dose regimens). From Week 16 onwards, three different maintenance treatment doses are to be tested. The trial design is illustrated in [Figure 3.1: 1](#).

Approximately 140 eligible patients with Palmoplantar Pustulosis will be randomised in a 2:1:1:1:2 ratio to one of the 5 following treatment arms:

Arm 1: BI 655130	 (N=40)
Arm 2: BI 655130	 (N=20)
Arm 3: BI 655130	 (N=20)
Arm 4: BI 655130	 (N=20)
Arm 5: Placebo	 (N=40)

The randomisation will be stratified for Japan versus non-Japan and will be done to assure that sufficient patients per treatment arm are recruited specifically within each region (Japan vs non-Japan). Screening of patients into any single region (Japan or non-Japan) will be closed in order to ensure that not more than 91 patients are randomised into that region. The rationale is to allow for a thorough assessment in the Japanese population and to assess whether there is a difference in treatment effect between Japanese vs non-Japanese patients (which is hypothesized based on clinical trials in Japan which tend to show larger treatment effects in PPP patients than have been observed in European clinical trials). This stratum will be included into the analyses of the primary endpoint.

 This is required to keep the blinding. Please refer to [Sections 4.1.1](#) and [4.1.5.1](#) for details.

An overview of all relevant trial activities is provided in the [Flow Chart](#). For visit schedules and details of trial procedures at selected visits, refer to [Sections 6.1](#) and [6.2](#), respectively.

The patients are followed-up until Week 68 which is 16 weeks after the last dose of the study drug at week 52 (Residual Effect Period of 16 weeks).

[figure not shown]

Figure 3.1: 1 Trial design

An independent Data Monitoring Committee will evaluate safety and efficacy data on a continuous basis. For details please refer to [Section 8.7](#).

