6. GENERAL ANALYSIS DEFINITIONS

6.1 TREATMENTS

For more details of study information on the treatment to be administered, assignment to treatment, and selection of dose, refer to Section 4 of the CTP.

The following study phases are defined:

Table 6.1: 1 Flow chart of analysis phases

Study analysis phase	Description	Start (included)	End (included)
Screening phase	Screening	Earliest of (Date of informed consent, first screening procedure)	Date/time of start of the first study dose minus 1 minute.
Loading treatment phase	On-treatment period	Date/time of start of the first study loading dose (Day 1)	Earlier of: i) Date/time of start of the first maintenance dose; or, ii) Date of end of last loading dose + 112 days at 11:59 p.m. if patient early discontinued study treatment before the first maintenance dose
Maintenance treatment phase (primary analysis at week 16)		Date/time of start of the first study maintenance dose (if applicable)	Earlier of: i) Date/time of start of the first maintenance dose at or after week 16; or, ii) Date of end of last maintenance dose + 112 days at 11:59 p.m. if patient early discontinued study treatment before week 16
Maintenance treatment phase (post primary analysis at week 16)		Date/time of start of the first maintenance dose at or after week 16 (if applicable)	Earlier of: i) Date/time of start of first dose in OLE 1368.24 trial; or, ii) Date of end of last study maintenance dose + 112 days at 11:59 p.m.
Follow-up ¹ phase (if applicable)	Off-treatment period (if applicable)	Date of end of last study dose + 113 days at 0:00 a.m.	Latest of: i) Date of EOS visit; ii) end date on trial termination page at 11:59 p.m. iii) Date/time of start of first dose in OLE 1368.24 trial;

Dates are defined individually per patient. If more than one date is associated with a specific visit, measurements associated with a specific date are assigned to a study analysis phase according to the rules specified in the table. An analysis phase will not extend beyond the start date of the following phase.

¹ The off-treatment period (i.e. Follow-up phase) only exists if the trial completion date is after the date of end of last administration + 112 days.

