7.8.3 Vital signs

The analyses of vital signs (blood pressure, pulse rate), body temperature, and body weight will be descriptive in nature. In primary analysis, descriptive statistics of vital signs and for the difference from baseline (see [Section 6.7](#)) up to week 16 will be provided based on SAF, including the last value, the minimum value and the maximum value up to week 16. In final analysis, descriptive statistics of vital signs and for the difference from baseline (see [Section 6.7](#)) for all visits will be provided based on SAF, including the last value, the minimum value and the maximum value on treatment for Arm 1-4 and, up to and post the first treatment at or after week 16 respectively for Arm 5.

Clinically relevant findings in vital signs data will be reported as baseline conditions (at screening) or as AEs (during the trial) if judged clinically relevant by the investigator, and will be analysed as such.

[figure not shown]

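### Final-analysis laboratory and vital-sign minima and maxima cover the whole treatment period for Arms 1-4 but only about 16 weeks for placebo, so the active arms look more extreme even with no drug effect

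*SAP*

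**What the plan says.** **Final analysis, laboratory data (SAP 7.8.2).** The per-patient summaries are the last, minimum and "maximum value on treatment period for Arm 1-4 and, up to and post the first treatment at or after week 16". The sentence ends by assigning the split to Arm 5.

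**Final analysis, vital signs (SAP 7.8.3).** The rule is the same: "maximum value on treatment for Arm 1-4 and, up to and post the first treatment at or after week 16 respectively for Arm 5".

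**Final analysis, RCTC shift tables (SAP 7.8.2, laboratory data only).** "the last measurement and the worst graded will be counted by the period up to and post the first treatment at or after week 16", again for Arm 5. Nothing is said about Arms 1-4.

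**Which values count (SAP 6.7).** "The derivation of the last value, minimum value and maximum value of laboratory and vital signs data will consider all on-treatment values" within the period of interest, whether or not they were selected for a visit window.

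**How long on-treatment lasts (SAP Table 6.1: 1).** It ends at "Date of end of last study maintenance dose + 112 days at 11:59 p.m", or at the first dose in the extension trial if that comes earlier. Protocol 3.1 adds: "The patients are followed-up until Week 68 which is 16 weeks after the last dose of the study drug at week 52".

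**What the SAP does elsewhere.** The Week 16 analysis summarises last, minimum and maximum up to Week 16 without distinguishing arms (7.8.2, 7.8.3). In the final analysis, adverse events and possibly clinically significant laboratory abnormalities are separated, for every arm, into before and after the first maintenance treatment at or after Week 16 (7.8). The whole-period adverse event tables leave out Arm 5 (7.8).

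**The concern.** Arm 5 has to be split because it moves to active drug at Week 16. Arms 1-4 are not split, so the placebo summary and the active summaries cover periods of very different length. Minimum, maximum and worst grade are extremes over a window. Adding visits can leave them unchanged or make them more extreme, but cannot pull them back. A longer window therefore produces an apparent excess in the active arms without any drug effect.

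Safety in this trial is judged by comparing descriptive columns; no testing is planned. A reader of the final report who sets the placebo figures against Arms 1-4 could take the excess for a safety signal. A reader who knows of the artefact could discount a real one. The same report would also contain abnormality tables with equal windows, so two laboratory outputs could disagree on active against placebo purely because of how they were windowed.

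**Working it through.** The plan states no figure for this, so there is nothing to reproduce first. The check uses the window lengths, the scheduled sample counts and the effect of those counts on an extreme.

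**1. Window length.** The last dose is at Week 52, Day 365 (Flow Chart). On-treatment ends 112 days later: 365 + 112 = Day 477, which is Week 68.
- Arms 1-4, no extension trial: about 68 weeks, and 68/16 = 4.25 times the placebo window.
- Arms 1-4, entering the extension: Week 52 is the last visit (SAP Table 6.7: 1, note D), and 52/16 = 3.25 times.
- Placebo: about 16 weeks. This is approximate, since the period ends at the first dose at or after Week 16, or at last dose + 112 days after early discontinuation.

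**2. Scheduled post-baseline observations (protocol Flow Chart).** Laboratory samples are taken before dosing (protocol 6.2.2), so the Week 16 sample belongs to the placebo period.

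| | Placebo period | Arms 1-4, to Week 52 | Arms 1-4, to Week 68 |
|---|---|---|---|
| Safety laboratory | 5 (Weeks 2, 4, 8, 12, 16) | 11 (adds 20, 24, 32, 40, 48, 52) | 13 (adds 60, 68) |
| Vital-sign visits | 7 | 16 | 18 |

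**3. Effect with no drug effect.** The documents give no abnormality rates or correlations, so these are assumptions: stable normal values, the same distribution in every arm, and a common correlation between any two values from one patient. Each case was simulated with 400,000 patients.

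Mean maximum change from baseline, laboratory schedule, in SD units (the minimum mirrors it):

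| Correlation | 5 samples | 11 samples | 13 samples |
|---|---|---|---|
| 0.5 | 0.82 | 1.12 | 1.18 |
| 0.7 | 0.64 | 0.87 | 0.91 |
| 0.8 | 0.52 | 0.71 | 0.75 |

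Patients below a grade limit at baseline with at least one later value above it, assuming 5% of values exceed the limit at any draw:

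| Correlation | 5 samples | 11 to 13 samples |
|---|---|---|
| 0.5 | 14% | 23-25% |
| 0.7 | 10% | 16-17% |
| 0.8 | 8% | 12-13% |

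With independent visits the chance of any value above the limit is 1 - (1 - p)^n. At p = 2% this is 1 - 0.98^5 = 9.6% for 5 samples and 1 - 0.98^13 = 23.1% for 13. The size depends on the assumptions; the direction does not.

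**4. Last value.** Its expected value is the same in both windows in this model. It is a Week 16 value for placebo and a Week 52 to 68 value for Arms 1-4 patients who complete treatment. It is therefore not comparable, but nothing pushes it in an adverse direction.

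**5. After the fix.** With Arms 1-4 also split at Week 16, every arm has 5 scheduled laboratory samples (7 vital-sign visits) in the first period. With no drug effect and equal follow-up, the excess is zero.

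**The case against.** The best case for the plan is that the fair comparison is already available. The Week 16 analysis has its own clinical trial report with equal windows. The final report shows laboratory and vital-sign data by visit, so time-matched values up to Week 16 remain visible. Adverse events and possibly clinically significant laboratory abnormalities are split for all arms. Everything is descriptive, no decision rule uses these extremes, and reporting the full period for arms on active drug throughout is a reasonable descriptive aim. In a 20-patient arm, 10% against 16-17% is about 2 patients against 3 per parameter. The first-period tables would largely repeat the Week 16 report.

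All of that stands and limits the harm. It does not correct the unequal-window rule for the final-report summaries, and it does not explain why worst grade and clinically significant abnormality, both any-time-in-window measures, should be windowed differently.

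A reader might go further, and the documents do not support these steps:
- **That the last value is also biased against active treatment.** It differs in timing only.
- **That vital signs have a worst-grade table.** RCTC shift tables are planned for laboratory data only.
- **That the shift tables definitely use the whole period for Arms 1-4.** The sentence addresses Arm 5 alone. Whole-period counting for Arms 1-4 is the default implied by SAP 6.7 and by the general remark in SAP 7 that on-treatment data are reported; it is not a stated rule.
- **That placebo and active columns will stand side by side.** No table layouts are given, and SAP 6.1 provides separate labels for Arm 5 before and after the switch.

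**Conclusion.** The concern holds, within limits. For laboratory and vital-sign minimum and maximum in the final analysis, the unequal windows are explicit, and they make Arms 1-4 more extreme than placebo with no drug effect. Under the assumed correlations of 0.5 to 0.8, the excess in mean maximum laboratory change is about 0.2 to 0.4 SD (0.71 - 0.52 = 0.19 at the low end, 1.18 - 0.82 = 0.36 at the high end). For worst laboratory RCTC grade the same follows, but only if Arms 1-4 are counted over the whole period, which the SAP leaves unsaid. The last value is not comparable but carries no built-in direction.

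The trial's comparative safety assessment as a whole is not compromised: the Week 16 report and the split final-analysis tables give like-for-like comparisons. The fault lies in one group of descriptive final-report tables. It should be corrected because it is directional, avoidable and at odds with the SAP's own handling of adverse events.

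**What to change.** - **SAP 7.8.2:** derive last, minimum and maximum values and the RCTC shift tables (last and worst grade) for all five arms in two periods, up to and after the first treatment at or after Week 16. State the period for Arms 1-4 in the shift tables explicitly.
- **SAP 7.8.3:** do the same for last, minimum and maximum.
- **Comparison:** set placebo only against the first period of Arms 1-4.
- **Whole-period summaries:** show them, if wanted, for Arms 1-4 only and without a placebo column, as SAP 7.8 already does for adverse events.

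The cost is a wording change, one extra period flag in existing programs and somewhat more table output, part of which repeats the Week 16 report. No new data are needed.
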